GALDERMA LABORATORIES, L.P.

STATISTICAL ANALYSIS PLAN

Investigational Product: Sculptra® Aesthetic (injectable poly-L-lactic acid)

Protocol No.: GLI.04.SPR.US10321

Protocol Title: A Prospective, Open-Label, Multicenter Study to Evaluate the Long-

Term Safety of Sculptra®Aesthetic in Immuno-Competent Subjects

Stratified by Fitzpatrick Skin Type I-VI

Document Date: August 17, 2018

Version: Final 2.0

Galderma Laboratories, L.P. Protocol GLI.04.SPR.US10321

A Prospective, Open-Label, Multicenter Study to Evaluate the Long-Term Safety of Sculptra® Aesthetic in Immuno-Competent Subjects Stratified by Fitzpatrick Skin Type I-VI

SIGNATURE PAGE

This Statistical Analysis Plan has been prepared by:

Company / Title	Printed Name	Signature	Date
Prosoft Clinical / Senior Statistician	PPD		

This Statistical Analysis Plan has been reviewed and approved by:

Company / Title	Printed Name	Signature	Date
Prosoft Clinical / PPD	PPD		

Company / Title	Printed Name	Signature	Date
Q-Med /	PPD		
Sr. Biostatistician			

DOCUMENT HISTORY

Rev No	Date	Description	
1.0	29-Mar-2018	Original document	
2.0	17-Aug-2018	The following revisions were made to the statistical analysis plan:	
		Section 4.3: Broaden the definition of completer2 population to capture subjects who missed Year 2 visit but remained in the study beyond Day 703.	
		Section 4.4.4: Update for bullet 3 in Sensitivity Analyses, multiple imputation will be done separately for each of the following: injection site nodule and/or papule, and all other AEIs (excluding injection site nodules/papules).	
		Section 5.1: Add that unscheduled visit will not be used for analysis purposes in this study.	
		Section 5.2.1:	
		1. Clarify that when deciding on baseline characteristics to be used in multiple imputation models, two groups will be compared separately with subjects who remain in the study or have had an event of interest. One of these groups is subjects who discontinued without any injection site nodules and/or papules, and the other is subjects who discontinued without any AEI other than injection site nodules and/or papules.	
		2. Update that when conducting multiple imputations, AEIs will be divided into 2 distinct groups. One is injection site nodules and/or papules, and the other is any AEI other than injection site nodules and/or papules.	
		3. Continuous factor, number of injection sessions, will be tested using wilcoxon rank sum test, as the data is highly discrete.	
		4. Update the number of sets that will be imputed.	
		5. Update the algorithm used for multiple imputation.	
		6. Remove standard errors or CI from imputation estimates.	

	Section 5.4: Add section to clarify how duration and time to onset are calculated.
	Section 6.0: Add a deviation for the MI modeling.

Table of Contents

SIGNATURE PAGE	

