4.3.2 Safety populations

The analysis population for safety will include the ITT population and the PP population. The ITT population is the primary population for hypothesis testing. The Completer2 and Completer5 populations will be used for sensitivity analyses of the primary and secondary hypotheses.

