4.4.4 Analysis of safety data

4.4.4.2 Other analyses of adverse events

All adverse events will be collected and summarized with the number of subjects reporting adverse events by number of injections, system organ class, preferred term, severity, relationship to the Sculptra® Aesthetic, and relationship to injection procedure.

For injection site nodules and/or papules and any other AEI, summaries will also include incidence rates by location and intervention, duration (<=30 days versus >30 days), and time to onset (<=30 versus >30 days for nodules and/or papules, and <=120 versus >120 days for any other AEI). Duration and time to onset of all events will also be summarized with descriptive statistics. Kaplan Meier estimates and plots will also be provided to estimate the maximum duration and time to the first occurrence within a subject. Time to onset is defined as the time from first injection to the start of the event.

To obtain duration of injection site nodules and/or papules and any other AEI, events that are ongoing will be handled in two ways: 1) excluding events that are ongoing at the time of data cutoff; and 2) assigning data cutoff date as the event end date.

The following frequency distributions of adverse events (incidence tables) will be provided:

- Overview of adverse events
- All AEs by number of injection sessions
- All AEs by system organ class and preferred term by decreasing frequency
- All AEs by system organ class, preferred term and intensity
- All AEs by system organ class, preferred term and relationship to treatment
- All AEs by system organ class, preferred term and relationship to procedure

The following listings will be provided:

- All adverse events
- Serious adverse events
- Adverse events that lead to discontinuation of Sculptra® Aesthetic
- Adverse events that lead to discontinuation of study
- Injection site nodules and papules
- AEI, other than injection site nodule and papule

The incidence rate of injection site nodule and/or papule will also be summarized by study site and baseline wrinkle assessment.

Subject reported injection related events collected in the diary card will be summarized by frequencies and percentages. Severity of subject reported injection related events after initial treatment session will be summarized by anatomic areas and Fitzpatrick skin type groups.

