4.4.6 Interim analyses

Interim analyses will be conducted on all study variables at 4 time points:

- Following completion of all subjects Month 13 follow-up visits;
- Following completion of all subjects Year 2 follow-up visits;
- Following completion of all subjects Year 3 follow-up visits; and
- Following completion of all subjects Year 4 follow-up visits.

For these interim analyses, AEs and concomitant medications that started on or before the study visit will be included. If the study visit was not conducted, events/medications that started on or before the scheduled study day + 4 weeks (2 weeks for Month 13) will be included.

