5.2 Missing Data

5.2.1 Missing AEI data due to subject discontinuation

If a subject discontinues the study before 2 or 5 years without an adverse event of interest, the subject will be assumed to have no adverse events of interest between the date of discontinuation and the 2 or 5-year time point when conducting the formal hypothesis testing. A sensitivity analysis will be conducted using the multiple imputation method to impute an outcome for these subjects.

To better determine covariates that will be used to conduct multiple imputation for missing event, the subjects who remain in the study or have had an event of interest will be compared to those who drop out without any injection site nodules and/or papules (or any AEI other than injection site nodules and/or papules), with respect to baseline characteristics and number of injection sessions to assess if missing appears to be missing at random or missing completely at random. Baseline characteristics include demographics (age, gender, ethnicity and race), Fitzpatrick skin type and medical history. Continuous factors include age and number of injection sessions. Age will be compared using a two sample t-test. Number of injection sessions will be compared using a wilcoxon rank sum test, as the data is highly discrete. Categorical factors will be compared using Pearson's Chi-square test, with Fisher's exact test as an alternative when the cell counts are less than 5.

A listing of discontinuation reasons for subjects who discontinued without an injection site nodule and/or papule or any AEI other than injection site nodule and/or papule will be provided, to detail the reason for missing.

5.2.2 Rules for imputing stop dates for adverse event, subject reported event, and prior/concomitant therapy

The imputed stop date will be derived from the CRF event/therapy stop date. If the CRF stop date day, month, and year are not missing then the imputed stop date will equal the CRF stop date. If any part of the CRF stop date is missing, the following rules will be utilized to impute the stop date.

- If the event/therapy is ongoing, the stop date will be set to missing.
- Otherwise, if the year is missing, a) if the subject is still in the study and the study is ongoing, the event will be assumed to be ongoing, and stop date will be set to missing; b) if the subject has left the study, the stop date will be set to the subject's final study date.

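### SAP version 2.0 drops standard errors or confidence intervals from the multiple-imputation sensitivity estimates, so their precision is not visible beside the Year 2 and Year 5 tests

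*SAP*

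**What the plan says.** SAP 5.2.1 sets the rule for the formal tests: a subject who discontinues before Year 2 or Year 5 without an AEI is taken to have none up to that time point. It then adds the check on that rule: "A sensitivity analysis will be conducted using the multiple imputation method to impute an outcome for these subjects". The Protocol synopsis (Interim analysis) places the formal tests at Year 2 and Year 5.

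The SAP Document History lists what version 2.0 changed. For Section 4.4.4, "multiple imputation will be done separately for each of the following: injection site nodule and/or papule, and all other AEIs". For Section 5.2.1, item 6 reads "Remove standard errors or CI from imputation estimates". Items 4 and 5 of the same list say that the number of imputed sets and the algorithm changed as well ("Update the algorithm used for multiple imputation"), but neither appears in the public 5.2.1.

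The public 5.2.1 agrees with item 6: it gives no standard error, confidence interval or pooling rule for the MI. SAP 6.0 mentions the MI only to clarify which groups are compared when covariates are chosen. It gives no reason for dropping precision. The other sensitivity analyses that the public text ties to the hypotheses are in SAP 4.3.2: "The Completer2 and Completer5 populations will be used for sensitivity analyses of the primary and secondary hypotheses".

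**The concern.** Counting dropouts as event-free can only leave the estimated incidence of a safety event unchanged or lower it. MI is the visible analysis that replaces that assumption for exactly the subjects concerned, so it should show whether a conclusion at Year 2 or Year 5 depends on the rule.

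A bare MI point cannot do this properly. If it falls on the other side of the formal criterion, or close to it, the reader cannot tell whether the difference exceeds the noise. The between-imputation part of the variance cannot be recovered from the point estimate. The obvious substitute, the standard error of the formal analysis, treats all 863 outcomes as known and is too small for an analysis that imputes part of them.

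**Working it through.** **The plan's own figures.** Protocol 7.1 enrols 863 to keep 604 evaluable. 604/0.70 = 862.9, rounded up to 863, and 1 − 604/863 = 30.0%. The 30% is inferred; the public text does not state it. The pivotal nodule/papule incidence (Protocol 4) is 20/116 = 17.2%.

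**Assumptions, none of them in the plan.** Dropout is 30% by Year 5 and independent of events. Five-year incidence is 17.2%. Each event-free dropout is imputed from the event share of the known group (subjects who complete or have had an event). Onset is either even (constant hazard) or pivotal-like (exponential with mean 184 days, the midpoint of the mean onsets of 159 and 209 days in Protocol 4). Dropout falls all in year 1, at a constant rate, or all in year 5. The formal criterion is not public, so I size precision only. I size only Year 5, because the public text gives no Year 2 retention.

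**Simulation.** 1500 trials of 863 subjects per scenario, 20 imputations, pooled by Rubin's rules. SEs are in percentage points.

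| Onset, dropout | MI mean % | Pooled MI SE | No-event-rule % | Its SE | Ratio of its SE to MI SE | Binomial SE on 604 at MI mean |
|---|---|---|---|---|---|---|
| Even, year 1 | 17.86 | 1.56 | 12.59 | 1.13 | 0.72 | 1.56 |
| Even, constant | 20.05 | 1.61 | 14.52 | 1.20 | 0.75 | 1.63 |
| Even, year 5 | 22.41 | 1.65 | 16.73 | 1.27 | 0.77 | 1.70 |
| Pivotal-like, year 1 | 20.56 | 1.62 | 14.96 | 1.21 | 0.75 | 1.64 |
| Pivotal-like, constant | 22.23 | 1.65 | 16.58 | 1.26 | 0.76 | 1.69 |
| Pivotal-like, year 5 | 22.88 | 1.66 | 17.18 | 1.28 | 0.77 | 1.71 |

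**Hand check of the first row.**
- Event-free completers: 604 × (1 − 0.172) = 500.1. Observed events: 863 × 0.1259 = 108.7. Known group: 608.8, with event share 108.7/608.8 = 17.9%.
- SE on the known group: sqrt(0.179 × 0.821/608.8) = 1.55 points, against 1.56 pooled.
- No-event rule: sqrt(0.1259 × 0.8741/863) = 1.13 points.
- 604 completers: sqrt(0.1786 × 0.8214/604) = 1.56 points.

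**Hand check of the last row.** Known group: 500.1 + 863 × 0.1718 = 648.4, with share 22.9%. SE: sqrt(0.229 × 0.771/648.4) = 1.65 points, against 1.66 pooled.

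**Results.**
- 95% half-width left unreported: 1.96 × 1.56 = 3.06 to 1.96 × 1.66 = 3.25 points.
- Borrowing the no-event-rule SE: 1 − 1.28/1.66 = 23% to 1 − 1.13/1.56 = 28% too narrow.
- Using a binomial SE on 604: from equal (1.56 against 1.56) to 3% too wide (1.71 against 1.66). It works because the known group, about 609 to 648 subjects in these two rows, is close in size to the completers.

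The MI means serve only to size the SE. They follow from the assumed imputation model, and they do not predict what the trial's MI will give.

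**The case against.** Three objections have force.

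- **Part of the MI text is not public.** The number of imputations and the algorithm were updated but cannot be seen. A test decision, a range across imputations or another precision summary may sit beside them. This stands: the point is about what is visible, and one sentence from the sponsor could settle it. The removal itself is stated outright in the current version and does not depend on hidden text.
- **The interval can be approximated.** With the MI point and the number of completers, a reader gets within about 3% of the pooled SE under these assumptions. This also stands and keeps the harm modest. It does not replace a reported interval: the approximation relies on the assumed imputation model, and the reader would have to know to use 604 and not 863.
- **MI is secondary.** The primary analysis is the intent-to-treat test with dropouts counted as event-free, and the Protocol synopsis plans no study change after the interim analyses. This stands too: no formal decision rests on the MI.

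Two stronger readings are tempting.

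- A reader might infer that the plan fails to use Kaplan-Meier as a check on the hypotheses, because SAP 4.4.4.2 places it among the other adverse event analyses: "Kaplan Meier estimates and plots will also be provided to estimate the maximum duration and time to the first occurrence within a subject". The documents do not support that. Protocol 13.5.4.1, where these sensitivity analyses are described, is not public, and neither is the SAP 4.4.4 list in which MI is the third bullet. Kaplan-Meier may be in either.
- A reader might infer that the MI ignores the day of discontinuation and so overstates risk, because the visible covariate screen is made "with respect to baseline characteristics and number of injection sessions to assess if missing appears to be missing at random". That text describes how candidate covariates are compared, not the imputation model. The algorithm is not public, so no such bias can be shown.

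**Conclusion.** The point holds in a narrow form. Version 2.0 of the SAP removes standard errors or confidence intervals from the MI estimates, and the public 5.2.1 puts nothing in their place. Under the stated assumptions the missing precision is a Year 5 half-width of about 3.1 to 3.3 points. That is enough to matter if the MI point lies near the criterion, and the formal analysis's standard error understates it. Because the completer count gives a close approximation and the MI is a supporting analysis, this is a change to consider and not a threat to the primary result. The size depends on the inferred 30% dropout, its independence from events, the pivotal incidence, and an imputation model that the public text does not confirm.

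**What to change.** In SAP 5.2.1, restore a pooled (Rubin's rules) standard error and 95% confidence interval for each MI estimate: nodule and/or papule, and all other AEIs, each at Year 2 and Year 5. State that each is read against the criterion used in the corresponding formal test. If a replacement precision summary already exists, keep it beside the interval.

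The cost is a few lines of SAP wording and slightly more programming, since the imputed sets are generated anyway. Protocol 13.1 allows the plan to be revised until a final one is issued before database lock. The drawback for the sponsor is that an interval may look less favourable than a bare point estimate.

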6.0 DEVIATIONS FROM PROTOCOL

1.0 Introduction

The safety and effectiveness of Sculptra® Aesthetic for the treatment of nasolabial fold (NLF) wrinkles was evaluated in a randomized, evaluator blinded, parallel group, multicenter clinical trial in the US (Study DL6049-0301). Immuno-competent subjects with previously untreated NLF wrinkles with wrinkle assessment score (WAS) of 2 (shallow) to 4 (deep) participated in the study.

The experience with Sculptra® Aesthetic in immune-competent subjects with darker skin types (ie, Fitzpatrick types IV-VI, see Appendix I in the clinical study protocol), was limited in the above study (ie, 22 out of 116 subjects treated with Sculptra® Aesthetic had skin type IV-VI). Thus, the Sponsor has committed to perform this postapproval study (PAS) to assess the safety of Sculptra® Aesthetic on at least 100 evaluable subjects with Fitzpatrick skin type IV-VI (including at least 15 with Fitzpatrick skin type IV and 85 with Fitzpatrick skin type types V or VI) up to 5 years (ie, completion of the follow-up phase). This PAS, in conjunction with the above pivotal study, would provide significant information to confirm the safety of Sculptra® Aesthetic in darker skin types over a longer period of observation and to assess device-related long-term incidence of chronic inflammation.

2.0 Study Design

2.1 Description of the Protocol

This is prospective, open-label, multicenter US study to evaluate the long-term safety of Sculptra® Aesthetic in immuno-competent subjects stratified by Fitzpatrick skin types I-III, IV, and V-VI.

This clinical study will be conducted in the US with approximately 863 subjects at a minimum of 20 sites, with a planned minimum of 15 subjects per site.

2.2 Duration of Study

The study participation for each subject will be approximately 5 years in duration. Subjects will receive open-label treatment at the screening/initial treatment visit (Visit 1, Day 1 – 1st injection session). Subjects will continue to receive open-label treatment for up to 9 weeks (Visit 2, Week 3 [2nd injection session]; Visit 3, Week 6 [3rd injection session]; and Visit 4, Week 9 [4th injection session]) if needed and determined by the clinical study Investigator. Subjects will continue with follow-up visits at Months 3, 6, 9, and 13, and Years 2, 3, 4, and 5.

2.3 Interim Analyses

Interim analyses are planned following completion of all subjects' Month 13, Year 2, 3, and 4 follow-up visits. All safety and efficacy data up to the interim cut-off date will be cleaned, interim locked, analyzed and reported.

3.0 Study Objectives

3.1 Primary

The primary objective of the study is to assess the long-term safety of Sculptra® Aesthetic in immune-competent subjects as a single regimen for correction of WAS 2 to 4 NLF contour deficiencies and other facial wrinkles in which deep dermal grid pattern (cross-hatch) injection technique is appropriate, for the following variables:

[figure not shown]
- The incidence of nodule and papules in subjects with Fitzpatrick skin type I-VI.
- The incidence of other adverse events of interest (hypertrophic scarring, keloid formation, change in skin pigmentation at the site of injection compared to adjacent skin, granulomas, skin necrosis, hypersensitivity reactions, and unexpected changes in wrinkle contour) in subjects with Fitzpatrick skin type I-VI.

3.2 Secondary

Secondary objectives include the following:

- To evaluate the time to onset, duration, severity, relationship to Sculptra® Aesthetic and/or injection procedure, and outcome of all adverse events, including adverse events mentioned under the primary objectives, during the course of the study, by Fitzpatrick skin type.
- To evaluate the change in the WAS from baseline to post-treatment follow-up time points at Months 6, 13, and Years 2, 3, 4, and 5 in NLFs and other facial wrinkles.
- To evaluate Investigator/subject global evaluations at Months 6, 13, and Years 2, 3, 4, and 5.

4.0 Statistical Analysis

4.2 Analysis Variables

4.2.1 Demographic and baseline characteristics

Demographic and baseline characteristics will include subjects' sex, race/ethnicity, age, height, weight, Fitzpatrick classification skin type, medical history, prior and concomitant medications, wrinkle assessment and measurement at initial treatment for NLFs and other anatomic areas, and vital signs (sitting heart rate and blood pressure).

4.2.2 Safety variables

4.2.2.1 Adverse events

Adverse events (AEs) are defined as adverse events that develop or worsen during the ontreatment period (time from first dose of Sculptra® Aesthetic to the end of the study). All adverse events will be coded using the current version of MedDRA.

The injection site adverse events listed below are defined as **Adverse Events of Interest** (AEI) in this study.

- Injection Site Nodule
- Injection Site Papule
- Hypertrophic scarring
- Keloid formation
- Changes in the skin pigmentation at the site of injection compared to adjacent skin
- Granuloma (confirmed by a biopsy)
- Skin necrosis
- Hypersensitivity reactions
- Unexpected change in wrinkle contour

The co-primary safety endpoints are:

1. The percentage (incidence rate) of subjects with any injection site nodule and/or papule over 5 years.

- 2. The percentage (incidence rate) of subjects with any of the following injection site events over 5 years, and they are termed as AEI other than injection site nodule and/or papule:
 - Hypertrophic scarring
 - Keloid formation
 - Changes in the skin pigmentation at the site of injection compared to adjacent skin
 - Granuloma (confirmed by a biopsy)
 - Skin necrosis
 - Hypersensitivity reactions
 - Unexpected change in wrinkle contour

The secondary safety endpoints are:

- the percentages (incidence rate) of subjects with any injection site nodule and/or papule over 2 years
- the percentages (incidence rate) of subjects who experienced any AEI other than injection site nodule or papule over 2 years

Summaries on Adverse Events and Adverse Events of Interest only take into consideration of those events that are treatment emergent.

4.2.2.2 Laboratory safety variables

A urine pregnancy test for women of childbearing potential will be collected at Visit 1.

4.2.2.3 Vital signs and physical exam

Vitals signs (sitting heart rate and blood pressure) and physical examination (overall subject assessment and facial assessment) will only be collected at Visit 1 and considered as the baseline characteristics for each subject (see Section 4.4.1).

4.2.2.4 Other safety variables

Injection related events will be collected in the diary card through the study.

4.2.3 Efficacy variables

4.2.3.1 Primary efficacy variables

None

4.2.3.2 Secondary efficacy variables

The secondary efficacy endpoints are:

- Change from baseline to post-treatment follow-up time points in the WAS at Month 6, Month 13, and Years 2, 3, 4, and 5.
- Investigator/Subject Global Evaluations at Month 6, Month 13, and Years 2, 3, 4, and 5.

